## 7. HYPOTHESIS AND OBJECTIVES

### 7.1. Primary objective:

- To describe the baseline clinical characteristics of the population of patients who are long-term responders to axitinib and to identify clinical factors associated with a long-term response to axitinib.

*For the study, “long-term responders to axitinib” has been defined as patients with progression-free survival [PFS] of at least 9 months with the drug, and “patients refractory to axitinib” has been defined as patients with disease progression in the first assessment after the start of treatment [estimated PFS  $\leq$ 3 months]*

To meet the study objective, two groups of patients with extreme response to the drug will be compared: a group of patients with long-term responses to the drug (group of long-term responders to axitinib) compared to a group of patients with disease progression in the first assessment after starting treatment (group of patients refractory to axitinib), in which the association of the following clinical factors will be analysed with the benefit of the treatment;

- Age ( $\leq$ 65 years and  $>$ 65 years)
- Baseline ECOG/PS at the start of treatment for each line (0, 1 and  $\geq$ 2)
- Number of previous treatment lines (1, 2 and  $\geq$ 3)
- Previous nephrectomy (yes and no)
- MSKCC risk group (favourable, intermediate and poor)
- IMDC risk group (favourable, intermediate and poor)
- Change in the MSKCC or the IMDC risk group with respect to the previous line (yes vs no);
- Histology (100% clear cells, main component of clear cells, main component of non-clear cells, 100% non-clear cells).

- Duration of first-line with a TKI ( $\geq 12$  months,  $\leq 6$  months;  $\leq 3$  months)
- Better response with the TKI received in first-line (CR/PR, SD, DP)
- Number of metastatic locations (1, 2 and  $\geq 3$ );
- Site of metastases (CNS metastases [yes vs no]; lymph nodes [yes vs no]; lung [yes vs no]; liver [yes vs no]; bone [yes vs no])
- Baseline LDH levels  $\leq 1.5 \times \text{ULN}$  (yes vs no)
- Baseline Hgb levels  $> \text{LLN}$  (yes vs no)
- Baseline corrected  $\text{Ca}^{++}$  levels  $\leq 10$  mg/dl (yes vs no)
- Baseline neutrophil levels  $\leq \text{ULN}$  (yes vs no)
- Baseline platelet levels  $\leq \text{ULN}$  (yes vs no)
- Neutrophil/lymphocyte ratio  $\leq 3$  (yes vs no)
- Smoking habits (smoker, non-smoker or ex-smoker)

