**Inclusion criteria**

Patients must meet all the inclusion criteria below to be eligible for inclusion in the study:

1. IC1: Evidence of a personally signed and dated informed consent document indicating that the patient (or his/her legal representative) has been informed of all relevant aspects of the study. Informed consent will only be obtained from patients who are still alive.
2. IC2: Aged 18 or over.
3. IC3: Histologically confirmed diagnosis of advanced renal cell carcinoma, with at least one radiological evaluation of the disease according to RECIST 1.1 criteria.
4. IC4: Treatment with axitinib, as second-line or further line treatment and with progression-free survival PFS of 9 months or more or with disease progression at the first response assessment.

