**Analysis population****All analyses will be performed with evaluable patients.**

The CRF contains the information related to the eligibility criteria as binary variable (Yes/No) for each of the described items.

Several of these criteria can be verified with the data recorded in the CRF. This verification is performed in order to prevent the inclusion of non-evaluable participants in the statistical report and prior to the start of any analysis.

These patients will be considered screening failure, and in the statistical report they will thus be included in a table of patient disposition together with the patients screening failure initially confirmed by the sponsor.

The criteria to be verified in the patient CRFs to define the evaluable population are described below:

- An "evaluable" patient must have received at least one dose of axitinib prior to inclusion in the study: it must be verified that the "Starting dose" and the "Treatment start date with axitinib" have been specified in "Treatment with axitinib". This date must be prior to the date of signing the informed consent (for patients who are still alive at enrolment).

- Inclusion requirement *Patients must have received axitinib as second-line treatment or further line*: it must be verified that there is information concerning a first-line treatment in the "First-line treatment" section.

- IC1: *Evidence of a personally signed and dated informed consent document indicating that the patient (or his/her legal representative) has been informed of all relevant aspects of the study. Informed consent will only be obtained from patients who are still alive.*

It must be verified that the date of signing the informed consent is specified (for patients who are still alive at enrolment).

Noted that for patients already dead before the study inclusion, the CII could be "No".

- IC2: *Aged 18 or over.*

It must be verified that the age calculated with respect to the date of the baseline visit is  $\geq 18$  years.

- IC3: *Histologically confirmed diagnosis of advanced renal cell carcinoma, with at least one radiological evaluation of the disease according to RECIST 1.1 criteria.*

It must be verified that the following data have been indicated: Date of first diagnosis, Tumour stage at disease diagnosis, Date of advanced disease diagnosis, Stage of advanced disease, Metastasis location, Best treatment response (first-line treatment).

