Risk groups are defined considering the following five factors (Favourable, Intermediate, Poor):

- ECOG/PS <1 (related to KPS <80)
- Time from first Diagnosis to Systemic Treatment less than 1 year
- LDH >1.5 x ULN
- Corrected calcium >10 mg/dl
- Haemoglobin < LLN

---

The risk groups are as follows:

- Favourable: 0 factors
  - Intermediate: 1 or 2 factors
  - Poor: >2 factors
- 
- Heng (or IMDC) risk group (described in appendix 11.1.). It will be analysed “at the beginning of the axitinib treatment” and “on the axitinib discontinuation”. These calculations will be performed on patients who have data on all the variables involved (in the case of a patient who does not have data on all the variables but has > 2 factors, it will be classified in the “Poor” risk group.

Risk groups are defined taking into account the following six factors (Low, Intermediate, High):

- ECOG/PS <1 (related to KPS <80)
- Time from first Diagnosis to Systemic Treatment less than 1 year
- Corrected calcium >10 mg/dl
- Haemoglobin < LLN
- Neutrophils > ULN
- Platelets > ULN

The risk groups are as follows:

- Favourable: 0 factors
  - Intermediate: 1 or 2 factors
  - Poor: >2 factors
- 
- Risk group according to MSKCC Criteria for patients previously treated with a TKI (defined in appendix 11.1). It will be analysed “at the beginning of the axitinib treatment”. Of note, all patients must have been previously treated with a TKI. These calculations will be performed on patients who have data on all the variables involved (in the case of a patient who does not have data on all the variables but has > 2 factors, it will be classified in the “Poor” risk group.

Risk groups are defined taking into account the following three factors (Low, Intermediate, High):

- ECOG/PS <1 (related to KPS <80)
- Haemoglobin < LLN
- Corrected calcium >10 mg/dl

The risk groups are as follows:

- Favourable: 0 factors
- Intermediate: 1 factor
- Poor: 2 or 3 factors
- The Objective Response Rate (ORR) is the frequency of subjects with CR or PR.
- The Clinical Benefit Rate is the frequency of subjects with CR, PR or SD.
- Increase of the axitinib dose to above 5 mg twice daily. Defined as having specified "Increase" at least one time, and in this case having specified "New dose" >5 mg/12h.
- Reduction of the axitinib dose to below 5 mg twice daily. Defined as having specified "Reduction" at least one time, and in this case having specified "New dose" <5 mg/12h.

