## 7.1 PRIMARY OBJECTIVE

In order to meet the study's primary objective, the baseline clinical characteristics of two patient groups with extreme response to the drug will be compared: A group of patients with long-term responses to the drug (long-term responders to axitinib) versus a group of patients with disease progression at the first assessment after the initiation of treatment (group of patients refractory to axitinib).

The classification (in long-term responders or refractory patients) will be based on PFS (in months), as indicated in section 5.2.

It will be shown the following descriptive tables:

- “Long responder” patient (Yes, No). “Long responding patient” is defined if he / she has an PFS  $\geq 9$  months (during axitinib treatment). The 95% CI will be displayed.
- PFS in long responding patients. Only the descriptive analysis of the time in months and the CI for the average, will be shown.
- “Refractory” patient (Yes, No). "Refractory patient" is defined if there is a better response to treatment = PE (to axitinib treatment). 95% CI will be shown.
- PFS in refractory patients. Only the descriptive analysis of the time in months and the CI for the average will be shown.
- Patient group (Long respondent, refractory). It is defined in section 5.2. IC95% will be displayed

At the same time, In addition to comparisons of baseline clinical characteristics between the groups (long-term responders, refractory patients), an association analysis of the following factors with the study groups will be performed:

- Age with respect to first visit ( $\leq 65$  years and  $> 65$  years).
- Age with respect to first diagnosis ( $\leq 65$  years and  $> 65$  years).
- Age with respect to start of axitinib ( $\leq 65$  years and  $> 65$  years).
- Baseline ECOG/PS and at the initiation of first line treatment (0, 1 and  $\geq 2$ ).
- Baseline ECOG/PS and at the initiation axitinib treatment (0, 1 and  $\geq 2$ ).
- Baseline ECOG/PS and at the end of axitinib treatment (0, 1 and  $\geq 2$ ).
- Number of previous treatment lines
- Number of previous treatment lines (1, 2 and  $\geq 3$ )
- Previous nephrectomy (yes and no)
- MSKCC (or IMDC) risk group in all moments in which it is analysed during the study (favourable, intermediate and poor)

- Histology (100% clear cells, primarily clear cells, primarily non-clear cells, 100% non-clear cells)
- Duration of first-line treatment

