- Duration of first-line treatment:([0-3] months, [3-6] months, [6-9] months, [9-12] months,  $\geq 12$  months).
- Duration of first-line treatment: ( $\leq 9$ months,  $>9$  months).
- Duration of first-line treatment: ( $\leq 12$ months,  $>12$  months).
- Duration of first-line TKi treatment: ([0-3] months, [3-6] months, [6-9] months, [9-12] months,  $\geq 12$  months).

It will be calculated the duration of the first line, if the drug was only a TKi.

- Duration of first-line TKi treatment: ( $\leq 9$ months,  $>9$  months).
- Duration of first-line TKi treatment: ( $\leq 12$ months,  $>12$  months).
- Duration of the first TKI treatment:( [0-3] months, [3-6] months, [6-9] months, [9-12] months,  $\geq 12$  months).

It will be calculated the duration of the first treatment with a TKi, in 1st or later line (always after axitinib).

- Patients treated with a TKi previous to axitinib other than first. It will be analysed the number of patients with a TKi previous to axitinib, different from the first TKi received.

It will be analysed the duration of this treatment.

- Best response with the TKI received in the first-line (CR, PR, SD, DP)
- Best response with a TKi previous to axitinib with a TKi other than first line (CR, PR, SD, PD).
- Best response with line prior to axitinib with a TKI if a line prior to axitinib other than the first one has been received (CR/PR, SD, DP).
- Number of metastatic locations (1, 2 and  $\geq 3$ ); See this definition in section 7 Definitions of variables and objectives.
- Site of metastases (CNS metastases [yes vs no]; lymph nodes [yes vs no]; lung [yes vs no]; liver [yes vs no]; bone [yes vs no]). In addition to showing the descriptive and comparative table of metastatic locations between groups, another similar table will be shown but with the categories “Hepatic” and “Bone” united in a single.
- Neutrophil/lymphocyte ratio  $\leq 3$  (yes vs no). See this definition in section 7 Definitions of variables and objectives. It will be analysed in all moments included in the study.
- Line of treatment in which it was received.

- 
- Presence of comorbidities.
  - Suspension of treatment.
  - Have you received any further treatment?
  - Has there been disease progression?
  - Best response to treatment (RC, RP, EE, PE).
  - Best response to treatment (RC / RP, EE, PE).
  - Duration of axitinib treatment.
  - Vital status

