  - Baseline LDH levels  $>1.5 \times \text{ULN}$  (yes vs no). At the beginning of 1st line
  - Baseline Hgb levels  $\leq \text{LLN}$  (yes vs no). At the beginning of 1st line
  - Baseline corrected Ca++ levels  $>10$  mg/dl (yes vs no). At the beginning of 1st line
  - Baseline neutrophil levels  $> \text{ULN}$  (yes vs no). At the beginning of 1st line
  - Baseline platelet levels  $> \text{ULN}$  (yes vs no). At the beginning of 1st line
  - Smoking habits (smoker, non-smoker or former smoker). At the beginning of 1st line
  - Baseline LDH levels  $>1.5 \times \text{ULN}$  (yes vs no). At the beginning of axitinib treatment
  - Baseline Hgb levels  $\leq \text{LLN}$  (yes vs no). At the beginning of axitinib treatment
  - Baseline corrected Ca++ levels  $>10$  mg/dl (yes vs no). At the beginning of axitinib treatment
  - Baseline neutrophil levels  $> \text{ULN}$  (yes vs no). At the beginning of axitinib treatment
  - Baseline platelet levels  $> \text{ULN}$  (yes vs no). At the beginning of axitinib treatment
  - Smoking habits (smoker, non-smoker or former smoker). At the beginning of axitinib treatment

A logistic regression model will then be carried out to study the association between belonging to each of the two extreme treatment response groups, with each of the possible clinical factors of interest, prior to axitinib treatment. That is, those baseline factors (prior to the start with axitinib) that have been studied in section 7 and that are significant ( $P < 0.05$ ) or close to significance ( $P < 0.15$ ).

The factors in this situation will be summarized below, and that potential prognostic factors of the response to axitinib treatment (long responding group vs refractory group) are considered.

---

The optimal model of prognostic factors will be constructed with the variables that are finally significant ( $P < 0.05$ ).

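### SAP 7.1 ties the duration of the first TKI to treatment after axitinib; as written the item is either empty or not a baseline factor, and it should refer to treatment before axitinib

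*SAP*

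**What the plan says.** SAP section 7.1 introduces its list of candidate factors by saying that "an association analysis of the following factors with the study groups will be performed". One item on the list is the duration of the first TKI, in five categories. Its explanatory note begins "It will be calculated the duration of the first treatment with a TKi" and places that treatment in first "or later line (always after axitinib". No other definition of this variable exists: SAP section 7 defines durations by line number only.

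The same section then describes a logistic regression of group membership "with each of the possible clinical factors of interest, prior to axitinib treatment". Candidates for it are the pre-axitinib factors that are significant or reach P < 0.15 in the preceding comparisons.

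The protocol's factor list (section 7.1) has a related entry, "Duration of first-line with a TKI".

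**The concern.** The item is named as treatment history, and its timing note points to the opposite side of axitinib. The note is an operative definition that tells a programmer which treatment records to pick.

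It can also be programmed. SAP section 6 shows that the CRF records drug, start date and end date for treatments given after axitinib, so code that took the first TKI after axitinib would run and return plausible durations. The error would then be hard to see in the output, because the table would carry the name of a prior-treatment factor.

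**Working it through.** No arithmetic decides this point. The check is whether the note can be true alongside the rest of the plan.

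**What the other sections fix**

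1. *Line of axitinib.* SAP 2.1 requires "IC4: Treatment with axitinib, as second-line or further line treatment and with progression-free survival PFS of 9 months or more" or progression at the first assessment. For every evaluable patient "it must be verified that there is information concerning a first-line treatment". A first-line treatment therefore always precedes axitinib, and a TKI in first line cannot come after it.
2. *Drug class.* Protocol 6.1.5 describes axitinib as a TKI. For any patient in the study, the first TKI ever received is therefore either a drug given before axitinib or axitinib itself.
3. *Earlier TKI exposure.* Under the second-line MSKCC score, SAP section 7 adds: "Of note, all patients must have been previously treated with a TKI".
4. *Neighbouring items.* The next entry in SAP 7.1 concerns a TKI given before axitinib that differs from the first one received, which places the first one before axitinib too.
5. *Model entry.* SAP 7.1 admits only factors from before axitinib start to the logistic regression.

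**Three ways to read the note**

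- *Literal: the patient's first TKI, given after axitinib.* By steps 1 and 2 no such record exists, so the variable is empty for everyone. This holds even if the statement in step 3 does not cover every patient.
- *The first TKI given after axitinib.* The value exists only for patients who stopped axitinib and then received another TKI. It is measured after axitinib, hence in general after the response that defines the two groups. Missing values would depend on stopping axitinib, surviving and being treated again, all of which are related to group. The documents do not allow the direction or size of that distortion to be worked out.
- *The first TKI given before axitinib.* The item is a proper baseline factor and agrees with steps 1 to 5.

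**How much of the plan is touched**

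SAP 7.1 lists four codings of first-line duration (continuous, five categories, a 9-month split, a 12-month split), three codings of first-line TKI duration (five categories and the same two splits), and this item: 4 + 3 + 1 = 8. One of the eight is affected. It would be one of nine if the duration of a later pre-axitinib TKI were also counted.

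The three first-line TKI codings implement the protocol entry and carry no timing error. The defective item is an addition made in the SAP. Where the first line was a TKI alone, its intended value repeats the five-category first-line TKI coding. It adds information mainly for patients whose first TKI came in second line or later, which means axitinib in third line or later.

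**The case against.** The strongest reply is that this is a slip of one word that nobody would follow. The sentence contradicts itself, its neighbours all refer to treatment before axitinib, and the SAP's English is uneven elsewhere. To produce a post-axitinib variable a programmer would have to ignore the words *first* and *1st line*. This carries weight, and a slip is the likeliest explanation. It does not settle the matter, because the documents do not confirm it and the faulty note is the only definition.

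The other counter-arguments concern scope, and they stand:

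- A reader might infer that a baseline factor specified in the protocol has been turned into a consequence of the outcome. The documents do not support this: the protocol factor is covered by three other items.
- A reader might infer that the prognostic model is contaminated. The restriction to pre-axitinib factors should keep a post-axitinib duration out of it.
- A place on the list does not by itself mark a variable as a baseline predictor. The same list openly includes ECOG at the end of axitinib, duration of axitinib, best response and vital status. This item differs only in that its name hides the timing.

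**Conclusion.** The definition is wrong as written and should be corrected. The direct harm is confined to one univariate comparison.

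There is a secondary effect on one candidate factor. If the variable is recognised as post-axitinib, the model filter removes it, and with it the only coding that covers the duration of a first TKI given beyond first line. If it is taken by its name as history, it could be screened at P < 0.15 as though it were baseline. No sample size, error rate or protocol-specified analysis is shown to change.

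The conclusion rests on two assumptions: that the intended meaning is *before axitinib*, which is likely but unconfirmed, and that the filter is applied according to a variable's definition and not its label.

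**What to change.** - Redefine the item as *the duration of the first TKI received in any line before axitinib start*.
- State that patients with no TKI before axitinib are not applicable for this item. Such patients are possible despite the statement that all had an earlier TKI: protocol 6.1.4 gives an indication that includes failure of cytokines, and SAP section 7 has an *Others* group for first-line drugs. Without the rule, code that takes the first TKI could return axitinib itself for them.
- Add a programming check that the end date of the selected TKI is not after the axitinib start date. List exceptions for query and do not drop them automatically, because SAP section 8 replaces incomplete dates with mid-month or mid-year values.
- Mark which entries on the SAP 7.1 list are pre-axitinib and so may enter the logistic regression.
- Confirm which rule was used in any code already run. SAP section 1 records that the 24 October 2019 amendment followed a review of draft results, so code may exist.

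The cost is one sentence, one date check, a mark against each listed factor, and a look at existing code. If that code used post-axitinib records, one table and the candidate list for the model would need to be rerun.

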 $(\text{Dose increase date or Dose reduction date} - \text{Start date of treatment with axitinib}) / 30.4375$
  - Duration (months) of subsequent treatments =  
 $(\text{Date of end of subsequent treatment or of latest follow-up if not suspended} - \text{Date of start of subsequent treatment}) / 30.4375$ . In the case of several subsequent treatments per patient, proceed as follows: the duration in months of each of the subsequent treatments will be calculated (from the start date to the end date or last check if it continues). This will be done for all subsequent treatments and then proceed to make the sum per patient of all durations of subsequent treatments

- Progression-Free Survival (PFS, in months) =  
 (Date of Disease Progression on treatment with axitinib or death from any cause – Date of start of treatment with axitinib) / 30.4375  
 If there is no progression or death, the case is censored as  
 PFS (months) = (Date of latest follow-up – Date of start of treatment with axitinib) / 30.4375
- Time to progression (TTP, in months) =  
 (Date of Disease Progression – Date of start of treatment with axitinib) / 30.4375  
 If there is no progression, the case is censored as  
 TTP (months) = (Date of latest follow-up – Date of start of treatment with axitinib) / 30.4375
- Overall Survival (OS, in months) = (Date of death – Date of start of treatment with axitinib) / 30.4375  
 If death has not occurred, the case is censored as  
 Overall Survival (OS, in months) = (Date of latest follow-up – Date of start of treatment with axitinib) / 30.4375
- Overall Survival since the start of first-line treatment (OS, in months) = (Date of death – Date of start of first-line treatment) / 30.4375  
 If death has not occurred, the case is censored as  
 Overall Survival (OS, in months) = (Date of latest follow-up – Start date of first treatment) / 30.4375
- Patient subgroups
  - A-Long-term responders: comprising patients with PFS  $\geq 9$  months.
  - B-Refractory (primary): comprising patients with best response to treatment = PD. This date is collected in the CRF form “axitinib treatment”.
- MSKCC risk group (described in appendix 11.1.). It will be analysed “Before the beginning of the first line”. These calculations will be performed on patients who have data on all the variables involved (in the case of a patient who does not have data on all the variables but has > 2 factors, it will be classified in the “Poor” risk group.

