## 9.2 STATISTICAL ANALYSES

### Primary objective

A descriptive analysis will be performed of the baseline clinical characteristics (clinical history of renal cell carcinoma, first-line treatment, other treatments prior to axitinib) of the population of patients who are long-term responders with axitinib, in those patients refractories to treatment, and overall.

The baseline clinical characteristics will be statistically compared according to membership to each one of the two extreme treatment response groups.

Efficacy variables will be analyzed and compared between groups of long responders and refractory patients: PFS, time to progression, overall survival, overall survival from the beginning of the 1st line. These analyzes will be added in the statistical report in the sections in which these same analyzes are shown for the total N of patients.

In addition, the association of clinical factors of interest with the benefit of treatment will be analysed by logistic regression (see point 7.1. Primary objective).

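### SAP 7.1 builds its optimal prognostic model from about 47 overlapping pre-axitinib codings, with no named selection method, no rule for choosing among codings and no internal validation

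*SAP*

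**What the plan says.** Protocol 7.1 lists the clinical factors to be compared between long-term responders and refractory patients. SAP 7.1 expands that list and then describes a logistic regression. Candidates are "those baseline factors (prior to the start with axitinib) that have been studied in section 7 and that are significant" at P<0.05 or near-significant at P<0.15, so the working entry threshold is P<0.15. For the result, "The optimal model of prognostic factors will be constructed with the variables that are finally significant" at P<0.05.

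SAP 9.1 refers back to 7.1 for the factors. SAP 9.2 repeats, under the primary objective, that "the association of clinical factors of interest with the benefit of treatment will be analysed by logistic regression". Neither names a forward, backward or single-fit rule, says which of several codings of one variable may enter, or plans a bootstrap, cross-validation or shrinkage. Stepwise selection and bootstrapping appear only in Appendix A1.3, inside an extract from a published prognostic study.

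Protocol 7.1 also lists "Change in the MSKCC or the IMDC risk group with respect to the previous line". SAP 7.1 has no coding for it. In SAP 7, the variable introduced as "MSKCC risk group (described in appendix 11.1" is the five-factor version, analysed before first line only. IMDC is analysed at axitinib start and discontinuation, and the three-factor modified MSKCC at axitinib start.

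**The concern.** Identifying factors associated with long response is half of the primary objective, and this regression is its only multivariable result. The procedure has two weaknesses.

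First, many candidates are one variable cut again, so the screen gives the same information several chances to pass. The overlap also harms true factors: another coding, or a risk group that contains the factor, can take its place.

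Second, the selection step is not defined. Two analysts following SAP 7.1 could fit all screened codings once or eliminate backwards, and report different models. The odds ratios and confidence intervals of either model would take no account of the selection. A reader who sees a model called optimal would give membership of it more weight than it can bear.

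**Working it through.** **Inputs.** About 60 patients (Protocol 8.5, SAP 2.1) at around 2:1 (Protocol abstract) gives 40 long-term responders and 20 refractory patients. Screen at P<0.15, keep at P<0.05 (SAP 7.1). The plan states no power, error rate or model-size figure to reproduce. Prevalences and correlations are not in the documents and are assumed.

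**Count, Protocol 7.1.** 18 single factors + 5 metastatic sites = 23.

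**Count, SAP 7.1, pre-axitinib items only.** Age at diagnosis and at axitinib start 2; ECOG 2; lines 3 (two forms of number of previous lines, plus "Line of treatment in which it was received"); nephrectomy 1; risk groups 3; histology 1; first-line or first-TKI duration 8; another prior TKI 2; best response to earlier treatment 3; number of sites 1; sites 5 + merged liver/bone 1; neutrophil/lymphocyte ratio 2; comorbidities 1; five laboratory values and smoking at two times 12. Sum = 47, or 46 if merged liver/bone is only a table. Age at the study visit and items at or after the end of axitinib are excluded.

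**Simple arithmetic, no true association.**
- Refractory patients per candidate: 20/47 = 0.43; 20/23 = 0.87.
- Expected to pass the screen: 47 × 0.15 = 7.1; 23 × 0.15 = 3.5.
- Chance of at least one P<0.05 if independent: 1 − 0.95^47 = 0.91; 1 − 0.95^23 = 0.69.

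**Simulation of the two-step rule, no true association, 40 vs 20.** Set A uses mixed variable types, risk groups built from their components and first-line/axitinib-start correlations of 0.3, 0.6 or 0.85. It screens by chi-squared, exact or rank test and leaves the three codings confined to patients with another prior TKI out of the model. Set B uses binary codings at about 40% prevalence with within-block correlation 0, 0.5 or 0.8 (independent for 23). Each setting has 500 to 1,000 runs. LR means likelihood-ratio selection. Entries are the share of studies keeping at least one false factor.

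| Candidates | Set | Forward | Backward | One joint fit |
|---|---|---|---|---|
| 46-47 codings | A | 83-88% (LR) | 85-90% (LR), 61-66% (Wald) | 37-41% |
| 47 codings | B | 87-90% | 87-94% | 65-80% |
| 23 protocol factors | A | 71% (LR) | 73% (LR), 52% (Wald) | 39% |
| 23 protocol factors | B | 71% | 72% | 63% |
| 20 (components, no risk groups) | A | 67% (LR) | 70% (LR), 50% (Wald) | 40% |
| 17 (risk groups, no components) | A | 61% (LR) | 64% (LR), 41% (Wald) | 33% |

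In Set B with 47 codings, the mean apparent AUC of the non-empty models is 0.71-0.79 although the true value is 0.50.

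**More patients do not help.** In Set A at correlation 0.6, going from 40/20 to 80/40 moves the shares from 83% to 86% (forward LR), 85% to 87% (backward LR), 61% to 74% (backward Wald) and 37% to 59% (one joint fit).

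**Change in risk group.** The CRF (SAP 6) holds risk criteria before first line, at axitinib start and at discontinuation, and none for intermediate lines. For second-line axitinib the previous line is the first line, and the components of five-factor MSKCC and of IMDC are recorded at both times. For axitinib in third line or later, the protocol's comparison cannot be made.

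**The case against.** The study is declared exploratory, with no hypotheses and no sample-size calculation (Protocol 8.5). SAP 4 openly plans no multiplicity adjustment, and SAP 9.2 puts the descriptive comparisons first. Entry and retention thresholds are stated. All of this stands, so a missing alpha correction is not the fault. An exploratory label still does not define a selection rule or justify calling the result optimal.

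The percentages rest on assumed inputs, and one joint fit gives 37-41% in one set and 65-80% in the other. This also stands: the direction is stable, the size is not. In Set A with one joint fit, shortening the list does almost nothing unless the risk-group components are dropped.

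A reader might infer more than the documents support:
- *The two line variables must pass or fail the screen together.* They carry the same information, but SAP 7.2 groups axitinib line as 2 or ≥3, so different tests and P-values are possible.
- *Codings were added once draft results were known.* SAP amendment 2 followed a review of draft results, but its summary mentions subgroups and methodology and names no coding.
- *Treatment after axitinib enters the model.* The words "or later line (always after axitinib" read as a slip: the next item speaks of a TKI before axitinib, and the model is restricted to earlier factors.
- *Vital status or axitinib duration could be selected.* They are on the comparison list, but the same restriction removes them from the model.

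**Conclusion.** The point holds and should be corrected, though the descriptive comparisons are unaffected. As written, membership of the final model is weak evidence. With about 60 patients at 2:1 and no true association, at least one false factor is kept in about 60-94% of studies with stepwise or backward selection and 37-80% with one joint fit. That spread reflects both the choice the SAP leaves open and the assumed prevalences and correlations.

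One coding per factor reduces the problem, to about 40-73% and 33-63%, without removing it. That is why the selection must also be named and its instability shown.

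For illustration only, with five factors truly associated (four binary at an assumed odds ratio of 2 or 3, plus first-line duration), 33-41% of kept terms were unrelated to any of them. Low haemoglobin at axitinib start with a true odds ratio of 3 was kept in 18-24% of studies with 47 codings and 37-39% with one coding per factor. These effect sizes are not in the documents, and the conclusion does not depend on them.

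Separately, the change-in-risk-group factor of Protocol 7.1 is missing from the SAP, and the CRF supports it only for second-line axitinib.

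**What to change.** 1. In SAP 7.1, admit to the multivariable model one prespecified coding per Protocol 7.1 factor, measured at axitinib start where available. Enter "Duration of first-line with a TKI" once, as continuous: the protocol's categories (≥12, ≤6, ≤3 months) overlap and leave 6 to 12 months uncovered. Say how patients whose first-line drug was not a TKI are handled. Use either risk groups or their components, not both.
2. Name the selection method. Repeat the whole screening and selection in bootstrap samples, report inclusion frequencies as a measure of stability, and state that the odds ratios and confidence intervals are not adjusted for selection.
3. Call the result a hypothesis-generating model. Report the other codings and cut-points as sensitivity analyses outside it, and keep every protocol factor in the univariate tables.
4. Report change in risk group univariately, on one scale computed at both times, for patients with second-line axitinib, and state that the CRF does not allow it for later lines.
5. Correct the wording slip about treatment after axitinib.

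The cost is SAP text and modest programming, possibly outside SPSS, with no new data. Protocol 8.7 calls for a protocol amendment if the sponsor regards this as a major change to the primary analysis. Fewer factors will be declared: in the illustrative scenario at an odds ratio of 3, a mean of 2.2 instead of 3.0 terms with forward LR and 1.7 instead of 2.3 with Wald elimination. The bootstrap will show instability but will not sort true from false factors well at this size. In that scenario, using the 20-factor list, median inclusion was 56% for related against 49% for unrelated kept factors with forward LR, and 49% against 46% with Wald.
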